Appendix B St. George's respiratory questionnaire

[figure not shown]

Appendix C SGRQ scoring algorithm

[figure not shown]

[figure not shown]

[figure not shown]
Appendix D EXACT questionnaire

Appendix E EQ-5D

Appendix F BODE

BODE Index for COPD

The BODE Index is a composite marker of disease taking into consideration the systemic nature of COPD (Celli et al., 2004).

Scoring the BODE Index

	0	1	2	3
FEV ₁ % pred	≥65	50-64	36-49	≤35
6MWD (m)	≥350	250-349	150-249	≤149
MMRC	0-1	2	3	4
BMI (kg.m ⁻²)	>21	≤21		

Total BODE Index score = 0 to 10 units

(FEV₁% pred = predicted amount as a percentage of the forced expiratory lung volume in one second; 6MWD = six minute walking distance; MMRC = modified medical research council dyspnea scale; BMI = body mass index)

Modified MRC Dyspnoea Scale	
0	Breathless only with strenuous exercise
1	Short of breath when hurrying on the level or walking up a slight hill
2	Slower than most people of the same age on the level because of breathlessness or have to stop for breath when walking at my own pace on the level
3	Stop for breath after walking about 100 meters or after a few minutes at my own pace on the level
4	Too breathless to leave the house or I am breathless when dressing

Appendix G High dose of inhaled corticosteroids: Adults

The following list of high dose of ICS is not a comprehensive list; the ICS that are not part of the list should be discussed with the Sponsor to confirm high vs. lower dose prior to randomization.

Inhaled corticosteroid	Daily dose (mcg)	
	High	Lower doses
Beclometasone dipropionate (CFC)	>1000	</=1000
Beclometasone dipropionate (HFA)	>400	</=400
Budesonide (DPI)	>800	</=800
Ciclesonide (HFA)	>320	</=320
Fluticasone propionate (DPI or HFA)	>500	</=500
Mometasone furoate	>440	</=440
Triamcinolone acetonide	>2000	</=2000

(Adapted from GINA 2014 Guidance)

High dose of inhaled corticosteroids: Adults (Japan)

Inhaled corticosteroid	Daily dose (mcg)	
	High dose	lower doses
Beclometasone dipropionate (HFA)	401-800	</= 400
Fluticasone propionate (HFA)	401-800	</=400
Ciclesonide (HFA)	401-800	</=400
Fluticasone propionate (DPI)	401-800	</=400
Budesonide (DPI)	801-1600	</=800
Budesonide inhalation suspension	1<x<=2	</=1.0

(Adapted from Japanese Asthma Prevention and Management Guideline 2018)

CFC – chlorofluorocarbon; HFA – hydrofluoroalkane; DPI – dry powder inhaler;

Appendix H Definition of anaphylaxis

“Anaphylaxis is a serious allergic reaction that is rapid in onset and may cause death.”

(Adapted from *Sampson HA, Munoz-Furlong A, Campbell RL, Adkinson NF, Bock SA, Branum A, et al. Second symposium on the definition and management of anaphylaxis: Summary report—Second National Institute of Allergy and Infectious Disease/Food Allergy and Anaphylaxis Network symposium. J Allergy Clin Immunol 2006;117: 391-7*)

Clinical criteria for diagnosing anaphylaxis

Anaphylaxis is highly likely when any one of the following 3 criteria are fulfilled:

1. Acute onset of an illness (minutes to several hours) with involvement of the skin, mucosal tissue, or both (eg, generalized hives, pruritus or flushing, swollen lips-tongue-uvula)
AND AT LEAST ONE OF THE FOLLOWING
 - a. Respiratory compromise (eg, dyspnea, wheeze-bronchospasm, stridor, reduced PEF, hypoxemia)
 - b. Reduced BP or associated symptoms of end-organ dysfunction (eg, hypotonia [collapse], syncope, incontinence)
2. Two or more of the following that occur rapidly after exposure to a *likely allergen for that patient* (minutes to several hours):
 - a. Involvement of the skin-mucosal tissue (eg, generalized hives, itch-flush, swollen lips-tongue-uvula)
 - b. Respiratory compromise (eg, dyspnea, wheeze-bronchospasm, stridor, reduced PEF, hypoxemia)
 - c. Reduced BP or associated symptoms (eg, hypotonia [collapse], syncope, incontinence)
 - d. Persistent gastrointestinal symptoms (eg, crampy abdominal pain, vomiting)
3. Reduced BP after exposure to *known allergen for that patient* (minutes to several hours):
 - a. Infants and children: low systolic BP (age specific) or greater than 30% decrease in systolic BP*
 - b. Adults: systolic BP of less than 90 mm Hg or greater than 30% decrease from that person's baseline

PEF, Peak expiratory flow; *BP*, blood pressure.

*Low systolic blood pressure for children is defined as less than 70 mm Hg from 1 month to 1 year, less than (70 mm Hg + [2 × age]) from 1 to 10 years, and less than 90 mm Hg from 11 to 17 years.

Anaphylaxis is highly likely when any one of the following 3 criteria are fulfilled:

1. Acute onset of an illness (minutes to several hours) with involvement of the skin, mucosal tissue, or both (eg, generalized hives, pruritus or flushing, swollen lips-tongue-uvula)
AND AT LEAST ONE OF THE FOLLOWING
 - a. Respiratory compromise (eg, dyspnea, wheeze-bronchospasm, stridor, reduced PEF, hypoxemia)
 - b. Reduced BP or associated symptoms of end-organ dysfunction (eg, hypotonia [collapse], syncope, incontinence)
2. Two or more of the following that occur rapidly after exposure to a *likely allergen for that patient* (minutes to several hours):
 - a. Involvement of the skin-mucosal tissue (eg, generalized hives, itch-flush, swollen lips-tongue-uvula)
 - b. Respiratory compromise (eg, dyspnea, wheeze-bronchospasm, stridor, reduced PEF, hypoxemia)
 - c. Reduced BP or associated symptoms (eg, hypotonia [collapse], syncope, incontinence)
 - d. Persistent gastrointestinal symptoms (eg, crampy abdominal pain, vomiting)
3. Reduced BP after exposure to *known allergen for that patient* (minutes to several hours):
 - a. Infants and children: low systolic BP (age specific) or greater than 30% decrease in systolic BP*
 - b. Adults: systolic BP of less than 90 mm Hg or greater than 30% decrease from that person's baseline

PEF, Peak expiratory flow; *BP*, blood pressure.

*Low systolic blood pressure for children is defined as less than 70 mm Hg from 1 month to 1 year, less than (70 mm Hg + [2 × age]) from 1 to 10 years, and less than 90 mm Hg from 11 to 17 years.

Appendix I List of opportunistic infections

- Aspergillosis
- Blastomyces dermatitidis (endemic in the south-eastern and south-central states US, along Mississippi and Ohio Rivers)
- Candidiasis – Note that all cases should be collected as AEs. only systemic or extensive mucosal or cutaneous candidiasis is considered opportunistic infections
- Coccidioides immitis (endemic south-western US and Central and South America)
- Cryptococcus
- Cytomegalovirus
- Herpes Simplex (disseminated)
- Herpes Zoster (disseminated; ophthalmic; involvement of 2 or more dermatomes)
- Histoplasmosis (pulmonary or disseminated; most common tropical areas Tennessee-Ohio-Mississippi river basins)
- Listeriosis
- Mycobacterium avium
- Nontuberculosis mycobacteria
- Pneumocystis pneumonia (PCP)

This list is indicative and not exhaustive

Appendix J Selection criteria for AE groupings

Grouping	Preferred Term Code	Preferred Term
Conjunctivitis	10001257	Adenoviral conjunctivitis
Conjunctivitis	10010725	Conjunctival irritation
Conjunctivitis	10010726	Conjunctival oedema
Conjunctivitis	10010736	Conjunctival ulcer
Conjunctivitis	10010741	Conjunctivitis
Conjunctivitis	10010744	Conjunctivitis allergic
Conjunctivitis	10010745	Conjunctivitis chlamydial
Conjunctivitis	10010749	Conjunctivitis gonococcal neonatal
Conjunctivitis	10010754	Conjunctivitis tuberculous
Conjunctivitis	10010755	Conjunctivitis viral
Conjunctivitis	10018258	Giant papillary conjunctivitis
Conjunctivitis	10021629	Inclusion conjunctivitis
Conjunctivitis	10030861	Ophthalmia neonatorum
Conjunctivitis	10048908	Seasonal allergy
Conjunctivitis	10049458	Herpes simplex virus conjunctivitis neonatal
Conjunctivitis	10051625	Conjunctival hyperaemia
Conjunctivitis	10053991	Inclusion conjunctivitis neonatal
Conjunctivitis	10061784	Conjunctivitis bacterial
Conjunctivitis	10062889	Pingueculitis
Conjunctivitis	10063669	Photoelectric conjunctivitis
Conjunctivitis	10067317	Oculorespiratory syndrome
Conjunctivitis	10067817	Acute haemorrhagic conjunctivitis
Conjunctivitis	10069166	Blebitis
Conjunctivitis	10071570	Ligneous conjunctivitis
Conjunctivitis	10074701	Noninfective conjunctivitis
Conjunctivitis	10075264	Oculoglandular syndrome
Conjunctivitis	10080825	Conjunctivitis fungal
Conjunctivitis	10084034	Conjunctival suffusion

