8.3.1 Adverse event of special interest

An adverse event of special interest (AESI) is an AE (serious or nonserious) of scientific and medical concern specific to the Sponsor's product or program, for which ongoing monitoring and immediate notification by the Investigator to the Sponsor is required. Such events may require further investigation in order to characterize and understand them. Adverse events of special interest may be added, modified or removed during a study by protocol amendment.

For these AESIs, the Sponsor will be informed immediately (ie, within 24 hours), per SAE notification described in Section 8.3.2, even if not fulfilling a seriousness criterion, using the corresponding pages in the CRF (to be sent) or screens in the e-CRF. If an SAE or any AESI of anaphylactic reactions or systemic allergic reactions that are related to IMP and require treatment, or severe injection site reactions lasting longer than 24 hours, occurs in a patient, blood samples should be collected for determination of functional dupilumab concentration, and ADA assessment at or near the onset and completion of the occurrence of the event, if possible (see Section 8.5.3 for details).

- Clinically symptomatic eosinophilia (or eosinophilia associated with clinical symptoms).
- Anaphylactic reactions or systemic allergic reactions that are related to IMP and require treatment (see Appendix 15, Section 10.15).
- Severe injection site reactions that last longer than 24 hours.
- Any infection meeting at least one of the following criteria:
 - Any serious infection (SAE).
 - Requires parenteral (intravenous, intramuscular, subcutaneous) antimicrobial therapy.
 - Requires oral antimicrobial therapy for longer than 2 weeks.
 - Is a parasitic infection.
 - Is an opportunistic infection (see Appendix 16, Section 10.16).

Note: antimicrobial therapy refers to antibiotic, antiviral, and antifungal agents

- Any severe type of conjunctivitis or blepharitis.
- Keratitis.
- Significant ALT elevation:
 - ALT >5 × the upper limit of normal (ULN) in patients with baseline ALT \leq 2 × ULN, or
 - ALT $> 8 \times ULN$ if baseline ALT $> 2 \times ULN$.
- Pregnancy of a female subject entered in a study as well as pregnancy occurring in a female partner of a male subject entered in a study with IMP/NIMP.

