AESI and other AE groupings	Incidence of each type of AESI and other AE groupings will be tabulated by treatment group. For each type of AESI, the following analysis will be generated. • A summary of the number (%) of patients with - Any TEAE. - Any SAE (regardless of treatment-emergent status). - Any treatment-emergent SAE. - Any AE leading to death. - Any TEAE leading to death. - Any TEAE leading permanent treatment discontinuation. - Any TEAE related to IMP reported by Investigator. - Number of patients with the TEAE per 100 patient-years. - Any TEAE by maximum intensity, corrective treatment, and final outcome. • Kaplan-Meier (K-M) estimates of probability of having at least one TEAE at specific time points, and K-M curve to depict the course of event onset over time. The method to identify AESIs and other AE groupings will be specified in the SAP.
Death	 The following deaths summaries will be generated: Number (%) of patients who died by study period (TEAE, on-study) summarized on the safety population by treatment received. Death in nonrandomized patients or randomized and not treated patients. Treatment-emergent AE leading to death (death as an outcome on the AE eCRF page as reported by the Investigator) by primary SOC, HLGT, HLT, and PT showing number (%) of patients sorted by internationally agreed order of SOC and alphabetic order of HLGT, HLT, and PT.

28-Oct-2023 Version number: 1

Endpoint	Statistical Analysis Methods
Laboratory parameters	Results and change from baseline for the parameters will be summarized by treatment group for baseline and each post baseline time point, endpoint, minimum and maximum value. Summary statistics will include number of patients, mean, standard deviation, median, Q1, Q3, minimum, and maximum.
	The following definitions will be applied to laboratory parameters.
	 The potentially clinically significant abnormality (PCSA) values are defined as abnormal values considered medically important by the Sponsor according to predefined criteria/thresholds based on literature review and defined by the Sponsor for clinical laboratory tests. PCSA criteria will determine which patients had at least 1 PCSA during the on-treatment period, taking into account all evaluations performed during the on-treatment period, including unscheduled or repeated evaluations. The number of all such patients will be the numerator for the
	on-treatment PCSA percentage.

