Clinically symptomatic eosinophilia (or eosinophilia associated with clinical symptoms)	HLT = 'Eosinophilic disorders' or PT = 'Eosinophil count increased' followed by blinded medical review for selection of relevant events
Any severe type of conjunctivitis	Based on PTs in (Appendix J) and "Severe" ticked in Adverse Events eCRF page
Any severe type of blepharitis	HLT as "Lid, lash and lacrimal infections, irritations and inflammations" and "Severe" ticked in Adverse Events eCRF page
Keratitis	PT in (keratitis, allergic keratitis, ulcerative keratitis, atopic keratoconjunctivitis, herpes ophthalmic, ophthalmic herpes simplex, corneal infection)
Significant ALT elevation	"ALT increase" was checked and "Is the event an AESI" was answered Yes on AE eCRF as reported by the investigator (ALT $>5 \times$ ULN in participants with baseline ALT $\leq 2 \times$ ULN; OR ALT $>8 \times$ ULN if baseline ALT $>2 \times$ ULN)

Other selected AE grouping

Injection site reactions	HLT = 'Injection site reactions'
Malignancy	Sub-SMQ (20000091)- Malignant or unspecified tumors
Conjunctivitis (narrow)	PT in (Conjunctivitis, Conjunctivitis allergic, Conjunctivitis bacterial, Conjunctivitis viral, Atopic keratoconjunctivitis)
Conjunctivitis (broad)	PT in (Conjunctivitis, Conjunctivitis allergic, Conjunctivitis bacterial, Conjunctivitis viral, Atopic keratoconjunctivitis, Blepharitis, Dry eye, Eye irritation, Eye pruritus, Lacrimation increased, Eye discharge, Foreign body sensation in eyes, Photophobia, Xerophthalmia, Ocular hyperaemia, Conjunctival hyperaemia)
Conjunctivitis (FDA)	PT in (Conjunctivitis, Conjunctivitis allergic, Conjunctivitis bacterial, Conjunctivitis viral, Eye irritation, Eye inflammation, Giant papillary conjunctivitis)
Helminthic infections	HLGT= "Helminthic disorder"
AEs related to COVID-19 illness	SMQ [20000237] – COVID-19 narrow

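### The severe-conjunctivitis AESI is selected from a term list that includes Seasonal allergy, so a severe event coded to that term counts as conjunctivitis with or without eye involvement

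*SAP*

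**What the plan says.** Protocol Section 8.3.1 lists the AESI as "Any severe type of conjunctivitis or blepharitis". Table 10 in Protocol Section 9.4.2 hands the selection rule to the SAP: "The method to identify AESIs and other AE groupings will be specified in the SAP". The SAP rule therefore governs.

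In SAP Table 2 (Section 2.1.4.1), the row "Any severe type of conjunctivitis" has two conditions. The first is "Based on PTs in (Appendix J". The second is that the severe box is "ticked in Adverse Events eCRF page". Nothing else is required.

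Appendix J holds a single grouping, Conjunctivitis, with 28 preferred terms. One of them is "Seasonal allergy", code 10048908.

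Table 2 also defines three other conjunctivitis groupings (narrow, broad and FDA) under the other selected AE groupings. None of the three contains this term.

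**The concern.** The protocol's AESI is an eye event, but the SAP rule can count an event with no eye component. The severity condition does not filter this out: Protocol Appendix 3 (Section 10.3) defines severe as a general intensity grade, based on interference with everyday activities and not tied to any organ.

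At stake is the accuracy of one derived safety count. SAP Section 2.4.5.1 uses that count in the per-AESI summaries, in a risk difference and a hazard ratio with 95% confidence intervals, and possibly in Kaplan-Meier estimates. A severe AESI may have few events, so a stray one could be noticeable in that row.

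**Working it through.** The documents give no figure to reproduce and no event rate to compute with. The check sets the relevant texts side by side.

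1. **Apply the rule literally.** Take an event with preferred term *Seasonal allergy* and intensity *severe*. The term is in Appendix J, so the first condition is met. The box is ticked, so the second is met. The event is a severe conjunctivitis AESI whatever its symptoms.

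2. **Look for a later filter.** Anaphylactic reaction (cases found by the algorithm), hypersensitivity and symptomatic eosinophilia each carry a blinded medical review in Table 2. For eosinophilia the wording is "followed by blinded medical review for selection of relevant events". The conjunctivitis row has no such step. SAP Section 2.4.5.1 also summarizes investigator-reported AESIs separately, but that table does not remove events from the derived count.

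3. **Compare with the SAP's own conjunctivitis groupings.**

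| List in the SAP | Terms | Contains Seasonal allergy? |
|---|---|---|
| Appendix J (severe AESI) | 28 | Yes |
| Conjunctivitis (narrow) | 5 | No |
| Conjunctivitis (broad) | 16 | No |
| Conjunctivitis (FDA) | 7 | No |

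The narrow list reads "PT in (Conjunctivitis, Conjunctivitis allergic, Conjunctivitis bacterial, Conjunctivitis viral, Atopic keratoconjunctivitis". The broad list adds 11 further terms (16 − 5 = 11), all eye conditions or eye symptoms.

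4. **Compare within Appendix J.** By their names, 27 of the 28 terms are eye conditions or eye-related syndromes (28 − 1 = 27). *Seasonal allergy* is the only exception, and no reason for including it is given.

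5. **Size.** If n is the number of true severe conjunctivitis events in an arm and m the number of severe *Seasonal allergy* events without eye involvement, the derived count is n + m and the relative inflation is m / n. The documents supply neither n nor m. If m = 0 nothing changes, and if n = 0 the ratio is undefined. No percentage can be given.

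6. **Atopic keratoconjunctivitis.** This term is in the narrow and broad groupings but not in Appendix J. The Keratitis row of Table 2, itself an AESI, names the term and sets no severity condition. Every such event is therefore already an AESI. Adding the term to Appendix J would place a severe case under two AESIs.

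**The case against.** The best defence is that the plan exposes the problem itself. SAP Section 2.4.5.1 gives the narrow, broad and FDA groupings the same summaries as the AESIs, including by maximum intensity, so severe conjunctivitis counts free of *Seasonal allergy* are already planned. All treatment-emergent events are tabulated by preferred term and by severity, and listed. SAP Section 2.4.5 describes the safety analysis as essentially descriptive. This stands: a stray event would be visible and separable. It would still sit in the AESI row and in that row's risk difference and hazard ratio.

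A second defence is that Appendix J may be a standard, deliberately sensitive list. It contains neonatal terms that cannot apply to patients aged 40 to 85. The documents do not show which reports code to *Seasonal allergy*, and some of those events could involve the eye. That supports the review option as an alternative to deletion. It does not support counting every such event.

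Third, the lack of medical review is not unusual: the rows for severe blepharitis, keratitis and serious infection have none either. Nor do the three other conjunctivitis groupings match one another. Both observations are fair. Absence of review or a mismatch between lists would not be a defect by itself; the defect is the term that does not name an eye condition.

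A reader might go further and infer that dupilumab would reduce seasonal allergy, so that misclassified events would gather in the placebo arm and mask an ocular signal. The documents do not support this. Protocol Section 2.3 claims benefit in atopic dermatitis, asthma, chronic rhinosinusitis with nasal polyposis and eosinophilic esophagitis, and makes no statement about seasonal allergy. The planned outputs above also tell against masking.

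**Conclusion.** The point holds in a limited form. As written, the SAP rule counts any severe event coded to *Seasonal allergy* as severe conjunctivitis, contrary to the protocol's eye-event AESI and out of line with all three of the SAP's other conjunctivitis groupings. This is a wrong entry in a selection rule, not a missing detail.

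The effect is confined to one derived AESI and to events graded severe. It is probably small and could be nil, and the direction of any between-arm effect is unknown. The conclusion rests on two assumptions: that the rule is programmed as stated, and that the preferred term means what its name says. It does not depend on any particular report, such as hay fever, being coded to this term. Efficacy analyses and type I error control are not touched.

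**What to change.** Delete the *Seasonal allergy* row (10048908) from Appendix J, leaving 27 terms. Alternatively, keep the row and add to Table 2 that an event with this term counts only when blinded medical review confirms eye involvement, as is already done for symptomatic eosinophilia. Leave Atopic keratoconjunctivitis where it is.

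Make the change before the interim database lock. Protocol Section 9.4 requires the SAP to be final by then, and under SAP Section 4 that lock becomes the primary analysis for all endpoints if efficacy is shown.

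Deletion costs one row in one appendix and needs no new data. The review option adds a small blinded check, limited to severe events with this one term.

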Appendix K Handling of missing data

Annualized rate of moderate or severe exacerbation events during the 52-Week period

- ***Pattern mixture model - multiple imputation (PMM-MI)***

Step 1. The 52-week observation period is partitioned into bi-weekly (2-week) segments.

By clinical definition, a patient can have at maximum 1 moderate or severe exacerbation event per two weeks. For each patient, his/her event count over 52 weeks is broken down into a series of binary outcomes across each of the 26 bi-weekly segments (52 weeks). In the analysis, for each patient, in each bi-weekly segment, an imputation flag (imputefl) will indicate whether the patient needs imputation in that segment.

Step 2. Estimation for the bi-weekly binary event probability using observed data

Within each bi-weekly segment, the logistic regression model will be fitted to the observed data to model coefficient estimates and the estimated variance-covariance matrix, with adjusting for the planned treatment group, region (pooled country), ICS dose at baseline (high dose ICS [yes/no]), smoking status at screening (current smokers or not), baseline disease severity (as % predicted post-bronchodilator FEV₁), and number of moderate or severe COPD exacerbation events within one year prior to the study (≤ 2 , 3, or ≥ 4). From the posterior distribution of the model coefficients, we randomly draw 40 sets of iid samples. As a result, for each patient and in each bi-weekly segment, 40 estimated probabilities can be obtained by using the 40 samples of coefficients and the patient's covariate values.

Step 3. Multiple Imputation of binary event by bi-weekly segment after study withdrawal

If a patient withdraws from the study at the kth ($1 \leq k < 14$) day of Segment i prior to Week 52, and experienced a moderate or severe exacerbation within the first k days, this patient will be considered as “observed” (imputefl=0) up to Segment i and will need imputations (imputefl=1) from Segment i+1 to Segment 26 (Week 52).

If a patient withdraws from the study at the kth ($1 \leq k < 14$) day of Segment i prior to Week 52, and has no moderate nor severe exacerbation in Segment i, this patient will be considered as “observed” (imputefl=0) up to Segment i-1 and will need imputations (imputefl=1) from Segment i to Segment 26 (Week 52).

For a patient who needs imputation from Segment i+1 to Segment 26, in each bi-weekly segment, 40 independent random samples will be respectively drawn from 40 estimated Bernoulli distributions, whose probabilities are obtained in Step 2.

For each patient who early withdraws from the study, 40 sets of complete event count data can be obtained by summing the observed event count prior to withdrawal and each series of imputed binary events after withdrawal up to Week 52.

Step 2 and 3 can be realized by using PROC MI in SAS. Sample code can be found below:

```
#  
surf#pl#gwd@gg#vhg@<;496;;#qlpsxwh@73#rxw@rxwgwdw>#  
e|#prqwk>#  
fodvv#rxwfrph#wuw34sq##fqw|ju4#lfv#frsgqxp>#  
prqrwrqh#uhj#+IHY4eo2ghwdlov,>#  
orj1vwlf#+rxwfrph@wuw34sq#fqw|ju4#lfv#vprnlqj#IHY4eo#  
frsgqxp2ghwdlov#GHVFHQGLQJ,>#  
ydu##fqw|ju4#lfv#vprnlqj#IHY4eo#wuw34sq#frsgqxp#rxwfrph>#  
uxq>#
```

Step 4. Combining MI results by Rubin's formula

A negative binomial model with the same set of covariates as in the primary analysis will be fitted with 40 sets of complete datasets obtained in Step 3, so as to obtain 40 sets of treatment effect estimates (in log-scale) and p-values accordingly. Log transformed observation duration will be the offset variable for patients who complete the 52-Week treatment/study period, and log transformed 52 weeks will be the offset variable for patients who discontinue the study before Visit 16 (Week 52). At last, the SAS MIANALYZE procedure will be used to generate statistical inferences by combining results (in log-scale) from the 40 analyses using Rubin's formula. These and their confidence interval limits are then exponentiated to derive relative rates. Of note, the rule will be applied on the log risks and log risk ratio.

Step 4 can be realized by using PROC MIANALYZE in SAS. Sample code can be found below

```
#  
surf#pldqdo|}h#gwd@uubfrqy>#  
e|#Odeho>#  
prghohiihf#Hvwlpdwh>#  
vwghuu#VwgHuu>#  
rgv#rxwsxw#SdudphwhuHvwlpdwhv@uubsrrohg>#  
uxq>#  
surf#pldqdo|}h#gwd@dhbfrqy>#  
e|#WUW34SQ>#  
prghohiihf#Hvwlpdwh>#  
vwghuu#VwgHuu>#  
rgv#rxwsxw#SdudphwhuHvwlpdwhv@dhubsrrohg>#  
uxq>#  
/* estimated RR and corresponding 95% CI */  
data pouttx;  
  
set uubsrrohg;  
if Parameter="txval";  
rr = exp(estimate);  
uxq>#
```

- ***Control-based PMM-MI***

All steps are the same as the aforementioned approach except in Step 2: the individual bi-weekly mean probability will be calculated based on observations in matching placebo arms only, with adjustment of missing observation duration.

- ***Tipping point analysis***

The tipping point analysis for severe exacerbation events will use the similar approach as PMM-MI with tipping values for the odds.

Step 1. Estimation for the bi-weekly binary event probability using observed data

Within each bi-weekly segment up to Week 52, the logistic regression model will be fitted to the observed data to obtain the model coefficient estimates and the estimated variance covariance matrix, with adjusting for the planned treatment group, region (pooled country), ICS dose at baseline (high dose ICS [yes/no]), smoking status at screening (current smokers or not), baseline disease severity (as % predicted post-bronchodilator FEV₁), and number of moderate or severe COPD exacerbation events within one year prior to the study (≤ 2 , 3, or ≥ 4). From the posterior distribution for the model coefficients, we randomly draw 40 sets of iid samples. As a result, for each patient and in each segment, 40 estimated binary event probabilities can be obtained by using the 40 samples of coefficients and the patient's covariate values.

Step 2. Tip on the bi-weekly binary odds (the probability of having an event in the segment over the probability of being event-free in the segment)

Within each segment, for the patients from the placebo group and need imputation in that segment, the estimated odds for binary event will be deflated by decreasing a positive amount; for the patients from the treatment group and need imputation in that segment, the estimated odds for binary event will be inflated by increasing a positive amount. After the deflation/inflation, 40 sets of binary event probabilities can be obtained for the placebo and treatment groups, respectively.

Step 3. Multiple Imputation of binary event by bi-weekly segment after study withdrawal

For a patient who needs imputation from Segment i+1 to Segment 26, in each segment, 40 independent random samples will be respectively drawn from 40 estimated Bernoulli distributions, whose probabilities are obtained in Step 2.

For each patient who early withdraws from the study, 40 sets of complete event count data can be obtained by summing the observed event count prior to withdrawal and each series of imputed binary events after withdrawal up to Week 52.

Step 4. A negative binomial model with the same set of covariates as in the primary analysis will be fitted to the 40 sets of complete datasets obtained in Step 3, so as to obtain 40 sets of treatment effect estimates and p-values accordingly. Log transformed observation duration will be the offset variable for patients who complete the 52-Week treatment/study period, and log transformed 52 weeks will be the offset variable for patients who discontinue the study before Visit 16 (Week 52). Then, the SAS MIANALYZE procedure will be used to generate statistical inferences by combining results from the 40 analyses using Rubin's formula.

Step 2, 3 and 4 will be repeated iteratively until the p-value for combined treatment effect of dupilumab compared to placebo estimated in Step 4 is >0.05 or the maximum applicable treatment effect has been reached.

Change from baseline in pre-BD FEV₁ at Week 12

- ***Pattern mixture model-multiple imputation (PMM-MI)***

Step 1. Monotone missing pattern was induced by Markov Chain Monte Carlo (MCMC) method using PROC MI: for patients who have missing values at intermediate visits, but have value at subsequent visits, the intermediate missing values were imputed assuming a multivariate normal distribution over observations from all visits. 40 datasets with a monotone missing pattern will be obtained using this method.

Step 2. For each of the imputed dataset with monotone missing pattern obtained in Step 1, the remaining missing data will be imputed using the regression method for the monotone pattern with adjustment for covariates including treatment groups, age, sex, height, region (pooled country), ICS dose at baseline (high dose ICS [yes/no]), smoking status at screening (current smokers or not), and baseline pre-BD FEV₁. All available data in the monotone missing pattern data will be used. 40 fully imputed datasets are obtained.

Step 3. Each of the 40 complete datasets will be analyzed using an ANCOVA model with change from baseline in pre-BD FEV₁ at Week 12 as the response variable, treatment, age, sex, height, region (pooled country), ICS dose at baseline (high dose ICS [yes/no]), smoking status at screening (current smokers or not), and baseline pre-BD FEV₁ value as covariates. Then the SAS MIANALYZE procedure will be used to generate statistical inferences by combining results from the 40 analyses using Rubin's formula.

- ***Tipping point analysis***

Step 1. 40 imputations will be performed to generate 40 completed data sets following Step 1 and 2 for PMM-MI.

Step 2. The imputed FEV₁ values in Dupilumab group are subtracted by a positive amount d for each imputed data sets.

Step 3. The imputed FEV₁ values in placebo group are added by a positive amount p for each imputed data sets.

Step 4. Change from baseline in pre-BD FEV₁ will be analyzed using the ANCOVA model as described in the PMM-MI for each of the 40 complete datasets. Then the SAS MIANALYZE procedure will be used to generate statistical inferences by combining results from the 40 analyses using Rubin's formula.

Step 2 and Step 3 will be repeated iteratively until the p-value for treatment effect of dupilumab compared to placebo estimated in Step 4 is >0.05 or the maximum applicable treatment effect has been reached.

